#### **4.6.2.1.3. *Systemic Hypersensitivity Reactions***

Hypersensitivity reactions are exaggerated or inappropriate immunologic responses occurring in response to an antigen or allergen. These can be systemic or localized. At all visits, participants will be evaluated by the investigator for signs and symptoms suggestive of hypersensitivity. Investigators will complete an CRF designed to record additional information about AEs suggestive of a hypersensitivity reaction. The TEAEs of hypersensitivity reactions were identified using

- *Anaphylactic reaction* SMQ (20000021; narrow terms)
- *Hypersensitivity* SMQ (20000214; narrow terms), and
- *Angioedema* SMQ (20000024; narrow terms).

The number and percentage of participants who reported a TEAE for the following will be analyzed

- Any narrow term from any 1 of the 3 SMQs indicated above (that is, combined search across narrow portions of all 3 SMQs)
- Any narrow term within each SMQ, separately (that is, narrow SMQ search)

Individual PTs that satisfied the query will appear in the summary in decreasing order of risk difference between the LY3209590 and insulin glargine group.

The analyses above are the starting point for medical interpretation of any apparent differences between treatment groups. For notable events, case review will be applied to make the final determination of whether an event is most accurately described as a potential hypersensitivity reaction to study treatment, or another event that is not clearly associated with study treatment administration. This judgment will be on the basis of totality of information available, including the content of a follow-up CRF collected for potential hypersensitivity events.

#### ***4.6.2.1.4. Injection Site Reactions***

Injection site reactions (ISR) are AEs localized to the immediate site of the administration of a medication. The evaluation of ISRs will be through the unsolicited reporting of ISR TEAEs and through the use of an Injection Site Reaction Follow-up Form completed by the investigator for each incidence of ISR. A summary of the number of participants with reported events meeting any of the following categories will be provided

- MedDRA HLT of Injection site reactions
- MedDRA HLT of Administration site reactions NEC
- Lipodystrophies and localized amyloidosis, as represented by PTs of
  - Lipoatrophy
  - Lipodystrophy acquired
  - Partial lipodystrophy
  - Lipohypertrophy
  - Sclerema, and
  - Cutaneous amyloidosis.

The summary will present the number of participants who reported

- at least 1 AE meeting any of the above categories
- any AE in each category, and
- any AE for each PT within a specific category.

The PTs will be listed for summary within each category in decreasing order of risk difference between the LY3209590 and insulin glargine group.

The additional data collected on the ISR follow-up forms will be summarized in 2 distinct ways:

1. at the participant-level (each participant contributes to totals at most once, regardless of the number of ISR events the participant experienced), and
2. at the event level (each separate event contributes to totals, regardless of whether the participant experienced multiple ISR events).

#### ***4.6.2.1.5. Neoplasms***

The TEAEs of neoplasms will be identified by narrow search using the MedDRA SMQ

- *Malignant tumours* SMQ (20000194, narrow terms), and
- *Tumours of unspecified malignancy* SMQ (20000195, narrow terms).

A summary will present any narrow term

- from any 1 of the 2 SMQs indicated above (that is, combined search across narrow portions of both SMQs), and
- within each SMQ, separately (that is, narrow SMQ search).

#### **4.6.2.1.6. *Diabetic Ketoacidosis (DKA)***

DKA will be searched by MedDRA PTs from all TEAEs. The number and percentage of participants experiencing treatment-emergent DKA will be summarized. The TEAEs of DKA will be identified using MedDRA PTs of

- Diabetic ketoacidosis
- Ketoacidosis
- Euglycaemic diabetic ketoacidosis
- Ketonuria
- Diabetic ketosis
- Diabetic ketoacidotic hyperglycaemic coma
- Ketosis
- Urine ketone body present
- Blood ketone body
- Blood ketone body increased
- Urine ketone body
- Blood ketone body present, and
- Lactic acidosis.

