#### **4.6.2.1.8. *Peripheral Edema***

Peripheral edema TEAEs will be identified by MedDRA PTs (See Section [6.8](#)). The number and percentage of participants experiencing treatment-emergent peripheral edema will be summarized by PT.

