## 6.8. Appendix 8: MedDRA PT for Peripheral Edema

The analysis of peripheral edema (Section 4.6.2.1.8) will be based on the TEAEs in the following terms:

- Acute pulmonary oedema
- Ascites
- Brain oedema
- Bronchial oedema
- Capillary leak syndrome
- Cerebral oedema management
- Compression garment application
- Cytotoxic oedema
- Effusion
- Fluid retention
- Gastrointestinal oedema
- Generalised oedema
- Gravitational oedema
- Hydraemia
- Hypervolaemia
- Hypoosmolar state
- Lipoedema
- Lymphoedema
- Negative pressure pulmonary oedema
- Non-cardiogenic pulmonary oedema
- Non-pitting oedema
- Oedema
- Oedema blister
- Oedema due to cardiac disease
- Oedema due to hepatic disease
- Oedema due to renal disease
- Oedema mucosal
- Oedema peripheral
- Pelvic fluid collection
- Pericardial effusion
- Perinephric collection
- Perinephric oedema
- Peripheral swelling
- Pleural effusion
- Pulmonary oedema
- Retroperitoneal effusion
- Retroperitoneal oedema
- Skin oedema
- Skin swelling
- Subdural effusion
- Swelling

- Visceral oedema

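### The planned count of participants with DKA pools 13 preferred terms, only four of which name ketoacidosis, so the figure is broader than its label; for peripheral edema the problem is one of labelling only.

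*SAP*

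**What the plan says.** **DKA.** SAP 4.6.2.1.6 plans one summary under one label: "The number and percentage of participants experiencing treatment-emergent DKA will be summarized". The case definition follows: "The TEAEs of DKA will be identified using MedDRA PTs of", and then 13 PTs. They include "Urine ketone body present" and "Lactic acidosis". The section says the search is made by PT. It does not say the result is displayed by PT.

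**Peripheral edema.** SAP 4.6.2.1.8 is worded differently: "The number and percentage of participants experiencing treatment-emergent peripheral edema will be summarized by PT". Appendix 8 (SAP 6.8) says the analysis "will be based on the TEAEs in the following terms" and lists 42 terms, among them "Acute pulmonary oedema" and "Negative pressure pulmonary oedema".

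**General rules.** The adverse event table in SAP 4.6.2 has safety topics of interest summarized by PT. SAP 4.6 makes Fisher's exact test, a risk difference and a 95% confidence interval the default for safety comparisons, with the safety population as denominator.

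**The concern.** A reader who sees a number and percentage of participants with treatment-emergent DKA will take it to mean ketoacidosis. Under this definition it means any of a group of ketone and acidosis terms. Two of the terms, blood ketone body and urine ketone body, name a test without saying that the result was abnormal. Lactic acidosis is a different condition.

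Such reports are plausible in this trial. Protocol 5.1 and 6.8.3 allow SGLT2 inhibitors and metformin as background therapy, and ketones are part of the urinalysis in Protocol 10.2. By default, the pooled figure would also carry a formal between-arm comparison under the DKA label.

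The SAP is tighter elsewhere. Hypersensitivity (4.6.2.1.3), neoplasms (4.6.2.1.5) and hypokalemia (4.6.2.1.9) use narrow search terms. Hypersensitivity adds case review of notable events, and injection site reactions (4.6.2.1.4) are shown overall, by category and by PT. Neither DKA nor peripheral edema has a narrow subset, category rows or case review.

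**Working it through.** The plan states no expected rate for either topic, so there is no figure to reproduce. The check is a count of terms and the arithmetic of one extra participant.

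**1. DKA terms (SAP 4.6.2.1.6)**

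| Group | Terms | Count |
|---|---|---|
| Name ketoacidosis | Diabetic ketoacidosis; Ketoacidosis; Euglycaemic diabetic ketoacidosis; Diabetic ketoacidotic hyperglycaemic coma | 4 |
| Ketosis or ketone finding | Ketonuria; Diabetic ketosis; Ketosis; Urine ketone body present; Urine ketone body; Blood ketone body; Blood ketone body increased; Blood ketone body present | 8 |
| Other acidosis | Lactic acidosis | 1 |

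4 + 8 + 1 = 13, so 9 of 13 terms (69%) do not name ketoacidosis. That is a share of search terms. It says nothing about the share of events.

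**2. Size per participant**

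SAP section 5 plans about 670 participants at 1:1, which is 670 / 2 = 335 per arm. I assume all of them enter the safety population. One participant whose only matching term is outside the four ketoacidosis terms adds 1 / 335 = 0.30 percentage points to that arm's pooled figure.

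**3. Range under assumed counts**

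Reported percentage = (participants with a ketoacidosis term + participants with only another listed term) / 335. All counts below are assumptions.

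| With a ketoacidosis term | Ketoacidosis only, % | Pooled, 0 others | Pooled, 1 other | Pooled, 2 others | Pooled, 5 others |
|---|---|---|---|---|---|
| 0 | 0.00 | 0.00 | 0.30 | 0.60 | 1.49 |
| 1 | 0.30 | 0.30 | 0.60 | 0.90 | 1.79 |
| 2 | 0.60 | 0.60 | 0.90 | 1.19 | 2.09 |
| 5 | 1.49 | 1.49 | 1.79 | 2.09 | 2.99 |

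The extra terms can raise the pooled figure but never lower it. With no such participant, the pooled and ketoacidosis-only figures agree.

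**4. Peripheral edema terms (Appendix 8)**

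Of 42 terms, 2 name a peripheral site (oedema peripheral, peripheral swelling). Another 18 name an internal organ or cavity, for example brain oedema, ascites, and pleural, pericardial and subdural effusion. The remaining 42 − 2 − 18 = 22 are mostly generalised, skin, cause-named or unspecified terms; one is a procedure (compression garment application). Because 4.6.2.1.8 summarizes by PT, each of these falls on its own correctly named row, and the oedema peripheral row is not changed by the others.

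**The case against.** **The components are visible anyway.** The table in SAP 4.6.2 requires a by-PT display for safety topics of interest, and all TEAEs and SAEs are also tabulated by PT within system organ class. The diabetic ketoacidosis row for each arm will therefore exist. This stands and limits the harm. It does not correct the pooled percentage or its default test once that figure is quoted alone. PT rows also cannot be added to give a participant count, because one participant may have more than one term.

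**A sensitive search is a legitimate choice.** The SAP uses broad terms for hepatic disorders (4.6.2.3) and medication errors (4.6.2.1.12). Cutting the DKA search to four terms could lose cases coded as diabetic ketosis or as raised blood ketones. This stands, so the search should be kept and only its label changed.

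**Both percentages are overstated.** A reader might infer this from the two lists. The documents do not support it. Edema is reported by PT with no expressly planned pooled row, and for DKA an excess appears only if someone has a non-ketoacidosis term and no ketoacidosis term. No rates are given.

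**The comparison is biased, or a difference could be hidden or created.** This too is tempting. The same search applies to both randomized arms, and background drugs must have been stable for 90 days before screening, so they should balance on average. Abnormal laboratory results count as adverse events only when the investigator judges them clinically significant (Protocol 10.3.1), and the laboratory list has no blood ketone test. What is lost is specificity, with no known direction.

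**Programme consistency.** The SAP refers to a programme-level plan that is not among the documents. Whether these lists come from it cannot be told.

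**Conclusion.** The point holds for DKA as a matter of definition and label. SAP 4.6.2.1.6 expressly plans a pooled participant count called treatment-emergent DKA, and its rule counts participants with no ketoacidosis term. The text is complete and would be programmed that way, so this is not a missing detail.

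The size is 0.30 percentage points per such participant. Under an assumed 0 to 5 such participants in an arm, the addition is 0 to 1.49 points. For an event that may be sparse, a few such reports could make up most of the pooled row, but whether any will occur is unknown.

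For peripheral edema, only the title is at issue. It would become a counting problem only if a pooled row over the whole Appendix 8 list were produced under the name peripheral edema.

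The importance is low. Neither topic is among the primary, secondary or tertiary endpoints in SAP 1.1, and neither affects error control.

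**What to change.** In SAP 4.6.2.1.6:

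- Keep the 13-term search and title its total *ketosis/acidosis-related events*.
- Add a participant-level *DKA* row based on the four ketoacidosis terms.
- Show ketosis or ketone findings (eight terms) and lactic acidosis as separate lines.
- State the by-PT display, as 4.6.2.1.7 and 4.6.2.1.8 already do.

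In SAP 4.6.2.1.8 and Appendix 8:

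- Retitle the group *oedema, effusions and fluid overload*.
- Do not label any pooled row over the full list *peripheral edema*.

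This costs some SAP wording and a few summary rows, needs no new data, and keeps the broad signal search intact. The ketoacidosis-only row will probably be sparse. The new titles should be aligned with the programme-level plan so that integrated summaries use the same groupings.

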#### **4.6.2.1.7. *Diabetic Retinopathy or Maculopathy***

Diabetic retinopathy or maculopathy will be searched by MedDRA PTs from all TEAEs. Section [6.7](#) (Appendix 7) lists the PTs that will be used to identify TEAEs of diabetic retinopathy or maculopathy. A summary of retinopathy or maculopathy by PT will be provided.

#### **4.6.2.1.8. *Peripheral Edema***

Peripheral edema TEAEs will be identified by MedDRA PTs (See Section [6.8](#)). The number and percentage of participants experiencing treatment-emergent peripheral edema will be summarized by PT.

#### **4.6.2.1.9. *Hypokalemia***

The TEAEs of hypokalemia will be identified by narrow terms in *Hypokalaemia* SMQ (20000233). A summary of the number of participants with reported TEAEs meeting the SMQ narrow search criteria by PT will be provided.

#### **4.6.2.1.10. *Hyperglycemia***

The study treatments were designed as the treatment of hyperglycemia for diabetes patients. Therefore, the hyperglycemia is usually not reported as an AE in diabetes studies. However, if a participant develops severe, persistent hyperglycemia after randomization, a rescue therapy will be considered. A listing of participants who receive rescue therapy will be provided.

#### **4.6.2.1.11. Major Adverse Cardiovascular Events (MACE)**

Potential cerebrocardiovascular events will be identified by the investigative site or by a medical review conducted by the sponsor or designee. A blinded external Clinical Event Committee will adjudicate the events in a consistent and unbiased manner. Events include

- death
- cardiac ischemic events including
  - myocardial infarction,
  - hospitalization for unstable angina
- cerebrovascular events including
  - stroke
  - transient ischemic attack.
- hospitalization for heart failure, and
- coronary revascularization procedure.

Only confirmed MACE by the adjudication committee will be considered as AESIs. A listing of MACE events reported by investigator, including reported term and adjudication results, will be provided.

#### **4.6.2.1.12. Medication Error of Interest**

Medication Errors of Interest (MEI) are defined as medication error AEs (SMQ 20000224 - narrow and broad terms) that meet the criteria of important protocol deviation (IPD) indicative of multiple doses, according to the Trial Issue Management Plan. These events are considered IPDs and of special interest because of their potential to impact participant's safety.

MEI AEs are categorized as IPDs of "Investigational Medicinal Product and/or Investigational Device." Screening and identification of MEI AEs will occur during routine review of the protocol deviations and trial level safety reviews.

The number and percentage of participants reported with MEI will be analyzed.

A listing of MEI will be provided. The listing will indicate if severe hypoglycemia or P-R hypoglycemia occurred after the MEI.

#### **4.6.2.2. Hypoglycemic Events**

##### **4.6.2.2.1. Participant-Reported Hypoglycemic Events**

The following types of hypoglycemic events will be derived in the analysis data sets: documented hypoglycemia as Level 1, Level 2, and Level 3 (severe hypoglycemia) according to definitions based on the American Diabetes Association criteria where

- Level 1: glucose <70 mg/dL (3.9 mmol/L) and  $\geq 54$  mg/dL (3.0 mmol/L).
- Level 2: glucose <54 mg/dL (3.0 mmol/L).
- Level 3: severe hypoglycemia (confirmed by the investigator to be an event that required assistance for treatment).

Level 2 and Level 3 events are considered clinically significant hypoglycemia. Therefore, the analysis on a composite of Level 2 and Level 3 (denoted as Level 2/3) hypoglycemia will also be conducted.

Hypoglycemic events will also be further classified into

- nocturnal hypoglycemia (occurs between midnight and 0600), and
- non-nocturnal hypoglycemia (occurs between 0600 and midnight).

If a hypoglycemic event is within 60 minutes of another hypoglycemic event, it is considered as a continuation of the previous event. If there are multiple hypoglycemic events within 60 minutes of each other, then all events will be combined into a single event, which has the

- earliest date time
- minimum glucose value, if applicable
- maximum severity (Level 1, 2 or 3)
- combined symptoms and outcomes
- time of nocturnal if any of the events is nocturnal

of the multiple hypoglycemic events.

The combined event starts from the first record with Level 1, 2 or 3, and ends when there are no more events for at least 60 minutes.

A sensitivity analysis will be done for selected hypoglycemic endpoints where all hypoglycemic events are considered one hypoglycemic event until a succeeding glucose value is  $\geq 70$  mg/dL.

The evaluation of potential persistent-recurrent hypoglycemic events will be through assessment of the clinically significant events confirmed by investigators based on clinical judgment and through events identified by a prespecified criteria (Section [4.6.2.1.2](#) and Appendix [9](#), Section [6.9](#)) using information based on the participant-reported hypoglycemia.

The details of planned analyses are provided in the table below.

Endpoint	Analysis Period	Statistical Method
Event rate of Level 1 hypoglycemic events (events/participant/year): • All documented	Baseline, 0-6, 0-12, 0-26, 12-26 weeks, post-treatment period	Negative binomial regression with treatment, baseline HbA1c and baseline Level 1 hypoglycemia rate as covariates, log (exposure/365.25 days) as the offset in the model.
Event rate of Level 2 hypoglycemic events (events/participant/year): • All documented	Baseline, 0-6, 0-12, 0-26, 12-26 weeks, post-treatment period	Negative binomial regression with treatment, baseline HbA1c and baseline Level 2 hypoglycemia rate as covariates, log (exposure/365.25 days) as the offset in the model.

Endpoint	Analysis Period	Statistical Method
Event rate of Level 3 hypoglycemic events (events/participant/year): 
 
• All documented
 
	Baseline, 0-26 weeks, post-treatment period	Negative binomial regression with treatment, baseline Level 3 hypoglycemia rate and baseline HbA1c as covariates, log (exposure/365.25 days) as the offset in the model.  If the number of events is too small to run the negative binomial regression, exposure adjusted rate calculated by total number of events divided by total exposure for individual patients) will be provided and the empirical method (see Appendix 11 (Section 6.11) for details) will be used for treatment comparison.
Event rate of Level 2/3 hypoglycemic events (events/participant/year): 
 
• All documented
 
• Nocturnal
 
• Non-nocturnal
 
	Baseline, 0-6, 0-12, 0-26, 12-26 weeks, post-treatment period	Negative binomial regression with treatment, baseline HbA1c and baseline hypoglycemia rate of the same hypoglycemia type as covariates, log (exposure/365.25 days) as the offset in the model.  The plots of the mean cumulative functions (MCFs) by each treatment arm will also be created. The population mean for cumulative number of events up to time t, $M(t)$ , will be estimated using a nonparametric estimation method described by Nelson (2003).
Incidence of Level 1 hypoglycemic events: 
 
• All documented
 
	Baseline, 0-6, 0-12, 0-26, 12-26 weeks, post-treatment period	Logistic regression with treatment, baseline HbA1c and baseline Level 1 hypoglycemia incidence as covariates.
Incidence of Level 2 hypoglycemic events: 
 
• All documented
 
	Baseline, 0-6, 0-12, 0-26, 12-26 weeks, post-treatment period	Logistic regression with treatment, baseline HbA1c and baseline Level 2 hypoglycemia incidence as covariates.
Incidence of Level 3 hypoglycemic events: 
 
• All documented
 
	Baseline, 0-26 weeks, post-treatment period	Logistic regression with treatment and baseline HbA1c as covariates.

Endpoint	Analysis Period	Statistical Method
Incidence of Level 2/3 hypoglycemic events: 
 
• All documented
 
• Nocturnal
 
• Non-nocturnal
 
	Baseline, 0-6, 0-12, 0-26, 12-26 weeks, post-treatment period	Logistic regression with treatment, baseline HbA1c and baseline hypoglycemia incidence of the same hypoglycemia type as covariates.
Potential Persistent-recurrent hypoglycemic events 
 
• Identified by investigator
 
• Identified by prespecified criteria (defined in Section 6.11)
 
	Safety analysis period (see definition in Section 4.6)	The number of participants with at least 1 event will be summarized and compared by Fisher's exact test. The number of events will also be provided. Listings of the events will also be provided.

Abbreviations: HbA1c = hemoglobin A1c; Level 2/3= Level 2 and Level 3 composite.

Note: The yearly hypoglycemia rate during defined period is calculated by number of hypoglycemic events within the period/number of days patient at risk within the period \*365.25. For rare events, 100 year rate will be provided. The hypoglycemia incidence during defined period indicates if the patient has at least 1 hypoglycemia event within the period (Yes/No).

Note: Group comparisons for hypoglycemia incidence and rate at baseline , baseline HbA1c is not included in the model.

Note: The hypoglycemia rate during the defined period is calculated by the number of hypoglycemia events within the period/number of days a participant is at risk within the period. The hypoglycemia incidence during the defined period indicates if the participant has at least 1 hypoglycemia event within the period (yes/no).

